8.3 ADVERSE EVENTS AND SERIOUS ADVERSE EVENTS

8.3.1 DEFINITION OF ADVERSE EVENTS (AE)

Adverse event means any untoward medical occurrence associated with the use of an intervention in humans, whether or not considered intervention-related (21 CFR 312.32 (a)).

8.3.2 DEFINITION OF SERIOUS ADVERSE EVENTS (SAE)

An adverse event (AE) or suspected adverse reaction is considered "serious" if, in the view of either the investigator or sponsor, it results in any of the following outcomes: death, a life-threatening adverse event, inpatient hospitalization or prolongation of existing hospitalization, a persistent or significant incapacity or substantial disruption of the ability to conduct normal life functions, or a congenital anomaly/birth defect. Important medical events that may not result in death, be life-threatening, or require hospitalization may be considered serious when, based upon appropriate medical judgment, they may jeopardize the participant and may require medical or surgical intervention to prevent one of the outcomes listed in this definition. Examples of such medical events include allergic bronchospasm requiring intensive treatment in an emergency room or at home, blood dyscrasias or convulsions that do not result in inpatient hospitalization, or the development of drug dependency or drug abuse.

8.3.3 CLASSIFICATION OF AN ADVERSE EVENT

8.3.3.1 SEVERITY OF EVENT

For adverse events (AEs) not included in the protocol defined grading system, the following guidelines will be used to describe severity.

- **Mild** – Events require minimal or no treatment and do not interfere with the participant's daily activities.
- **Moderate** – Events result in a low level of inconvenience or concern with the therapeutic measures. Moderate events may cause some interference with functioning.
- **Severe** – Events interrupt a participant's usual daily activity and may require systemic drug therapy or other treatment. Severe events are usually potentially life-threatening or incapacitating. Of note, the term "severe" does not necessarily equate to "serious".]

8.3.3.2 RELATIONSHIP TO STUDY INTERVENTION

All adverse events (AEs) must have their relationship to study intervention assessed by the clinician who examines and evaluates the participant based on temporal relationship and his/her clinical judgment. The degree of certainty about causality will be graded using the categories below. In a clinical trial, the study product must always be suspect.

- **Related** – The AE is known to occur with the study intervention, there is a reasonable possibility that the study intervention caused the AE, or there is a temporal relationship between the study intervention and event. Reasonable possibility means that there is evidence to suggest a causal relationship between the study intervention and the AE.

- **Not Related** – There is not a reasonable possibility that the administration of the study intervention caused the event, there is no temporal relationship between the study intervention and event onset, or an alternate etiology has been established.

8.3.3.3 EXPECTEDNESS

The Principal Investigator will be responsible for determining whether an adverse event (AE) is expected or unexpected. An AE will be considered unexpected if the nature, severity, or frequency of the event is not consistent with the risk information previously described for the study intervention.

8.3.4 TIME PERIOD AND FREQUENCY FOR EVENT ASSESSMENT AND FOLLOW-UP

The occurrence of an adverse event (AE) or serious adverse event (SAE) may come to the attention of study personnel during study visits and interviews of a study participant presenting for medical care, or upon review by a study monitor.

All AEs including local and systemic reactions not meeting the criteria for SAEs will be captured on the appropriate case report form (CRF). Information to be collected includes event description, time of onset, clinician's assessment of severity, relationship to study product (assessed only by those with the training and authority to make a diagnosis), and time of resolution/stabilization of the event. All AEs occurring while on study must be documented appropriately regardless of relationship. All AEs will be followed to adequate resolution.

Any medical condition that is present at the time that the participant is screened will be considered as baseline and not reported as an AE. However, if the study participant's condition deteriorates at any time during the study, it will be recorded as an AE.

Changes in the severity of an AE will be documented to allow an assessment of the duration of the event at each level of severity to be performed. AEs characterized as intermittent require documentation of onset and duration of each episode.

Study staff will record all reportable events with start dates occurring any time after informed consent is obtained until 7 (for non-serious AEs) or 30 days (for SAEs) after the last day of study participation. At each study visit, the investigator will inquire about the occurrence of AE/SAEs since the last visit. Events will be followed for outcome information until resolution or stabilization.

8.3.5 ADVERSE EVENT REPORTING

AEs will be reported to the study sponsor and the IRB within X 7 days of the study staff learning of the event.

8.3.6 SERIOUS ADVERSE EVENT REPORTING

The study clinician will immediately report to IRB any serious adverse event, whether or not considered study intervention related, including those listed in the protocol or investigator brochure and must include an assessment of whether there is a reasonable possibility that the study intervention caused the event. Study endpoints that are serious adverse events (e.g., all-cause mortality) must be reported

in accordance with the protocol unless there is evidence suggesting a causal relationship between the study intervention and the event (e.g., death from anaphylaxis). In that case, the investigator must immediately report the event to the IRB.

All serious adverse events (SAEs) will be followed until satisfactory resolution or until the site investigator deems the event to be chronic or the participant is stable. Other supporting documentation of the event may be requested by the Data Coordinating Center (DCC)/study sponsor and should be provided as soon as possible.

8.3.7 REPORTING EVENTS TO PARTICIPANTS

Not applicable

8.3.8 EVENTS OF SPECIAL INTEREST

Not applicable

8.4 UNANTICIPATED PROBLEMS

8.4.1 DEFINITION OF UNANTICIPATED PROBLEMS (UP)

The Office for Human Research Protections (OHRP) considers unanticipated problems involving risks to participants or others to include, in general, any incident, experience, or outcome that meets all of the following criteria:

- Unexpected in terms of nature, severity, or frequency given (a) the research procedures that are described in the protocol-related documents, such as the Institutional Review Board (IRB)-approved research protocol and informed consent document; and (b) the characteristics of the participant population being studied;
- Related or possibly related to participation in the research (“possibly related” means there is a reasonable possibility that the incident, experience, or outcome may have been caused by the procedures involved in the research); and
- Suggests that the research places participants or others at a greater risk of harm (including physical, psychological, economic, or social harm) than was previously known or recognized.

8.4.2 UNANTICIPATED PROBLEM REPORTING

The investigator will report unanticipated problems (UPs) to the reviewing Institutional Review Board (IRB) and to the Data Coordinating Center (DCC)/lead principal investigator (PI). The UP report will include the following information:

- Protocol identifying information: protocol title and number, PI's name, and the IRB project number;
- A detailed description of the event, incident, experience, or outcome;
- An explanation of the basis for determining that the event, incident, experience, or outcome represents an UP;
- A description of any changes to the protocol or other corrective actions that have been taken or are proposed in response to the UP.

To satisfy the requirement for prompt reporting, UPs will be reported using the following timeline:

- UPs that are serious adverse events (SAEs) will be reported to the IRB and to the DCC/study sponsor within <1 week > of the investigator becoming aware of the event.
- Any other UP will be reported to the IRB and to the DCC/study sponsor within <2 weeks> of the investigator becoming aware of the problem.
- All UPs should be reported to appropriate institutional officials (as required by an institution's written reporting procedures), the supporting agency head (or designee), and the Office for Human Research Protections (OHRP) within <2 weeks > of the IRB's receipt of the report of the problem from the investigator.]

9 STATISTICAL CONSIDERATIONS

9.1 STATISTICAL HYPOTHESES

Aim 1. Our preliminary study established that gait and rest tremor are important factors to determine whether patients benefit from 60Hz stimulation or high frequency stimulation (38). However, the degree to which stimulation parameters affect gait parameters is not well established. In Aim 1, we will test the *hypothesis* that certain gait parameters are differentially affected between 60Hz and high frequency STN-DBS at various electrode contact configurations. In addition, in our preliminary analysis, we observed a modest reduction in dopaminergic medications in patients on 60Hz stimulation (12). Hence, we will also test the *hypothesis* that for some patients, the addition of levodopa in combination with 60Hz stimulation produces a synergistic improvement in certain gait domains.

Aim 2. Our preliminary data suggested that there is a link between the patient's baseline motor symptomatology measured by the MDS-UPDRS III ratings and the best stimulation frequency (60 Hz or HFS) chosen for the patient based on intensive clinical evaluations, which remained unchanged for an average of 12 months. In Aim 2, we test the *hypothesis* that a subject's gait kinematics on 60Hz stimulation can be predicted with statistically significant accuracy using gait measurements on high frequency stimulation. In addition, we will test the *hypothesis* that the best stimulation frequency (60Hz or HFS stimulation), which yields improvement among various gait parameters, can be predicted using objective sensor data collected at baseline. We define baseline motor performance as the severity of motor symptoms in the levodopa OFF and ON state without stimulation. In the remainder of this proposal, for simplicity we refer to 60 Hz stimulation and high frequency stimulation (130-180Hz) as low frequency (LFS) and high frequency (HFS), respectively.

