The opal body sensors (APDM, Opal, Portland, OR) will be fixed to each subject's wrists, ankles, sternum and lumbar spine and the SAW task will be carried out by the research coordinator for each combination of low and high frequency stimulation for the four contact pairs (total of 8 trials with each contact pair being either LFS or HFS, exclusively; refer to Figure 1). The gait measurements will be the same as in Phase I. Bradykinesia and tremor assessments will be conducted for each combination of stimulation and contact pairs using the Kinesia inertial sensors (Great Lakes Technologies, OH) as well. Ratings of items 3.1, 3.3 (a-e), 3.9, 3.11, 3.12, 3.13 of MDS-UPDRS III will also be conducted for each stimulation-contact pairing. Following each stimulation parameter change, there will be a 10-minute latency before the gait task is conducted. The participants will be blinded to each stimulation change.

During condition (2), the stimulators will be turned off and subjects will be given 1.5 times their usual levodopa dose (up to 300mg) to ensure transition to the medication ON state. Retesting will be done 1 hour after the levodopa challenge (or sooner based on patient report and visual confirmation by physician). Gait, bradykinesia and tremor sensor assessments as well as MDS-UPDRS III rigidity and axial subscore ratings will be conducted in the same manner as condition (1). The participants will be blinded to stimulation changes. At the completion of Visit 2, participants will return to their initial programming settings and resume their medication regimen as per their standard of care. If participant fatigue develops, he/she will have the option to complete condition (2) on another visit within a 4 week time period.

Beginning September 2020, and until the COVID-19 pandemic has passed, all subjects who are not fully vaccinated against COVID-19 will be tested for COVID-19 prior to participation (as outlined in Section 10.2). As a result, remote consent will be employed during the COVID-19 pandemic (see Section 8.2). COVID-19 tests will be performed by nasopharyngeal swab at a Northwell facility, the cost of which will be billed to the study fund.

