9.4.2 ANALYSIS OF THE PRIMARY EFFICACY ENDPOINT(S)

Aim 1.1.

Using the analytical software of APDM, the SWAY and TUG algorithms included in the SAW test will calculate asymmetry and variability for: postural sway (RMS AP & ML planes), cadence (CN), gait cycle duration, gait speed (SN), swing, double support, elevation at midswing, foot strike angle, toe off angle, stance, step duration, stride length (LN), arm swing velocity, arm range of motion, turn angle, turn duration, and turn velocity. All data will be tested for normality with Shapiro-Wilk test. Linear mixed models with repeated measures (LMMRM) will be used to compare high and low frequency over all contact pairs in the levodopa-OFF state. Parameter estimation will be based on restricted maximum likelihood and the form of the covariance matrix will be chosen based on Akaike's Information Criteria and Schwarz' Bayesian Criterion. The Holm-Bonferroni method will be used to adjust for multiple comparisons for the 20 outcome measures.

Aim 1.2. To investigate levodopa's effects on the gait domains, we will include the data for levodopa-ON and add a binary variable for levodopa (on or off) to the LMMRM from Aim1.1.

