Aim 2.1. We will utilize the raw data collected during Phase II to develop regression models, under both ON and OFF medication states for all contact pairs. The top panel in Figure 2 presents the overview of Aim 2.1; the goal of this sub-Aim is to predict the gait parameters for patients on low frequency by using the gait sensor measurements obtained on high frequency. Additional independent variables/regressors include general patient/disease characteristics such as age, gender, and disease duration. We will also build models under both ON and OFF medications. To develop the regression models, we use non-linear regression analysis based on random forest (RF) classifier. RF is based on an ensemble of decision trees, referred to as a 'forest,' where predictions for any new observation are obtained from averaging the predictions of individual trees (56). Generally, RF models are not prone to overfitting and are robust against noisy or high-dimensional datasets (57). In addition, they are generally interpretable, allowing for further examination of results and easier subject subtyping with respect to symptomology. However, to assure that the RF based models are the best performing models, we also develop models based on some of the other machine learning techniques, such as neural networks (56), and use them as benchmarks. If needed, to improve model performance we will perform model building in RF models to identify and include the most important parameters (38). We will use techniques such as cross-validation (e.g., leave-one-out) and bootstrapping to examine the generalizability of the models and acquire confidence intervals for the predicted values. Lastly, we will compare the best performing models obtained for both ON and OFF medications and their most important contributing parameters to further investigate the interaction of medications and stimulation frequency.

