9.4.7 SUB-GROUP ANALYSES

The subgroup analyses will be analyzed based on age, gender, and disease duration for both primary and secondary endpoints.

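### Aim 1.2 states synergy of levodopa with 60 Hz in some patients, but its model has no frequency-by-levodopa term and so tests neither average synergy nor its variation between patients

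*Combined protocol and SAP*

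**What the plan says.** Section 9.1, under Aim 1, sets the hypothesis that "for some patients, the addition of levodopa in combination with 60Hz stimulation produces a synergistic improvement in certain gait domains". The synopsis (1.1) gives the same hypothesis without limiting it to some patients, and the Aim 1.2 objective speaks only of the influence of 60 Hz and levodopa on gait.

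The analysis is in 9.4.2. For Aim 1.1, "Linear mixed models with repeated measures (LMMRM) will be used to compare high and low frequency over all contact pairs in the levodopa-OFF state"; "the form of the covariance matrix will be chosen based on Akaike's Information Criteria and Schwarz' Bayesian Criterion"; and "The Holm-Bonferroni method will be used to adjust for multiple comparisons for the 20 outcome measures". For Aim 1.2 the plan brings in the levodopa-ON data and says it will "add a binary variable for levodopa (on or off) to the LMMRM from Aim1.1". It names no product term, patient-level slope, responder definition or test of heterogeneity.

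Three other places come near the question. Section 9.4.7 says "The subgroup analyses will be analyzed based on age, gender, and disease duration for both primary and secondary endpoints", with no model. Under Aim 2.1, the ON and OFF prediction models are compared "to further investigate the interaction of medications and stimulation frequency". Section 9.4.8 lists individual data. Section 9.4.9 marks exploratory analyses as not applicable.

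The design has replication within patients: section 4.1 describes a "total of 8 trials with each contact pair being either LFS or HFS, exclusively", repeated in the second medication state.

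**The concern.** Three questions must be kept apart.

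- Does levodopa change gait on average? A levodopa main effect answers this.
- Does levodopa add more at 60 Hz than at high frequency, on average? This needs a frequency-by-levodopa interaction.
- Does that extra gain occur in some patients and not in others? This needs the interaction to vary by patient.

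Section 9.1 asks the third question and the synopsis asks something close to the second. The Aim 1.2 model, as written, answers the first. A significant levodopa coefficient could be reported as support for synergy when it is not, and a null one says nothing about synergy. If the interaction is added but no patient-level term, a null average still cannot refute a subset effect and a positive average cannot show that only some patients respond. The average test can also be too liberal, because contact pairs within a patient would be treated as independent information on synergy.

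Variation between patients is part of the protocol's own reasoning. Section 2.2 says little is known about which patients respond, and 2.1 asks whether there are 60 Hz-responsive subtypes.

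**Working it through.** **The plan's own figure.** Section 9.2 uses a difference of 0.14 and a variance of 0.03: 15.79 × 0.03 / 0.14² = 24.2. The textbook factor 2(1.96 + 0.84)² = 15.68 gives 24.0. With 20% attrition, 24 / 0.8 = 30. The 24 reproduces, but it comes from a healthy-versus-Parkinson's difference in speed. No figure in the plan refers to synergy.

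**What the model as written estimates.** Let the cell means be HFS/off 0, 60 Hz/off a, HFS/on b and 60 Hz/on a + b + g, where g is the synergy. With balanced data, a model with main effects only estimates a + g/2 for frequency and b + g/2 for levodopa. With a = 0.2, b = 0.3 and g = 0.8 these are 0.6 and 0.7. In one simulated trial with these values the additive model returned 0.68 and 0.72, and the model with the interaction returned 0.33, 0.37 and g = 0.70. The additive model splits the synergy between the two main effects and has no coefficient for it.

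**Set-up once the interaction is added.** The documents give no standard deviation (SD) for this contrast and no responder share, so both are assumed. Take 24 patients and a trial noise SD of 1. The contrast at one contact pair combines four trials, so its variance is 4 and its SD is 2. A patient's mean over four pairs has SD 2/√4 = 1. Synergy below is in these units.

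**Standard error of the average.** Suppose 20% of patients have +2, 20% have −2 and the rest 0. The variance between patients is 0.4 × 4 = 1.6.

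- True variance of the average: 1.6/24 + 4/96 = 0.108.
- Variance if the 96 contact-pair contrasts are treated as independent: (1.6 + 4)/96 = 0.058.
- Ratio of standard errors: √(0.108/0.058) = 1.36.
- Actual two-sided rejection rate at nominal 5%: 1.96/1.36 = 1.44, which gives about 15%.

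Simulation gives 15% for this analysis, 16% with a random intercept only, and 15–18% across the simulations run. The test on patient means gives 5%.

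**Average test against variance test.** The average test is a one-sample t test on the patient means. The variance test is F = 4 × var(patient means) / within-patient variance on 23 and 72 df. There were 20,000 simulations per row, at the 5% level.

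| Synergy pattern | Average test | Variance test |
|---|---|---|
| None | 5% | 5% |
| All patients at 0.6 | 81% | 5% |
| 50% of patients at 0.8 | 42% | 12% |
| 50% at 1.6 | 84% | 46% |
| 25% at 0.8 | 14% | 10% |
| 25% at 1.6 | 33% | 34% |
| 25% at 2 | 42% | 53% |
| 25% at 3 | 57% | 90% |
| 15% at 3 | 27% | 72% |
| 20% at +2, 20% at −2 | 5% | 89% |
| 25% at −3 (worsening) | 57% | 90% |

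At 0.05/20 = 0.0025, the first Holm step for 20 outcomes, 25% at 3 gives 10% against 62%, and 25% at 2 gives 7% against 15%. The plan states the Holm adjustment under Aim 1.1 and does not say whether it covers Aim 1.2.

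The last row shows that the variance test has no direction: it rejects as often when the subset gets worse.

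**The case against.** The strongest reply is that the restriction to some patients appears in 9.1 only. Read with the synopsis and the Aim 1.2 objective, the target may be average synergy, and rewording one sentence would remove half of the mismatch. That stands, and the fix offers it. It does not help with the missing interaction, which average synergy needs as well.

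A second reply is that the authors surely intend an interaction, since Aim 2.1 speaks of one. They may. But Aim 2.1 compares prediction models and tests nothing, and the Aim 1.2 text names only the binary variable. Choosing the covariance form by information criteria could admit a patient-level slope, but none is named and no test is attached.

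A third reply is that contact pairs are not clean replicates. This also stands. Section 9.1 expects differences between contact configurations, 4.1 sets amplitude per contact, 6.3 states no randomised trial order, and repeat dosing (6.1.2) or a split visit (4.1) can produce drift within a patient. Drift that differs between patients can look like variation in synergy unless the model accounts for contact pair and time.

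Some stronger readings are tempting but unsupported:

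- A reader might infer that the plan already tests average synergy and misses only the subset. As written it tests neither.
- A reader might infer that a variance test is generally the more powerful one. The table shows the reverse for weak effects and for large responder shares.
- A reader might infer that the average test has no power whenever responses go both ways. That holds only if they cancel.
- A reader might infer that a null result would close the question of who benefits. The Aim 2 models, the subgroup analyses, the individual listings and the randomised trial foreseen in 2.1 keep it open, although none of them tests variation in synergy.

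**Conclusion.** The mismatch between hypothesis and model is real and follows from the text alone: no frequency-by-levodopa term is stated, so the Aim 1.2 analysis cannot answer 9.1 in either form. This should be corrected before analysis. The sample size of 24 is not at fault here; it was simply not derived for this question.

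The size of the gain from a patient-level analysis is uncertain. It is large for strong effects in a minority or for opposing effects (90% against 57%, and 89% against 5%), and absent for weak effects or large responder shares (10% against 14%, and 46% against 84%). These figures rest on assumed responder shares and effect sizes and on independent trial noise. The protection of the average test's standard error applies whenever synergy varies between patients. Its size, 15–18% instead of 5%, belongs to the scenarios assumed.

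**What to change.** In 9.4.2, Aim 1.2:

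1. Add the frequency-by-levodopa fixed interaction as the test of average synergy, word its result as an average, and state which multiplicity adjustment applies.
2. Add a patient-level random effect for that contrast. Include contact pair, and trial order or time since dose, so that contact differences or drift are not read as variation between patients.
3. As a supportive analysis, report the variance of the random effect with its interval and each patient's shrunken synergy estimate with its interval. Claim synergy in some patients only if there is evidence of variation and the patient-level estimates lie in the direction of improvement.
4. If step 3 is not wanted, reword 9.1 to average synergy, dropping the restriction as the synopsis does.

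The cost is SAP wording and a few model terms on data already planned, provided that trial order and dosing times are recorded. The downsides are one further analysis per gait parameter and an imprecise variance estimate with 24 to 30 patients.

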1 PROTOCOL SUMMARY

1.1 SYNOPSIS

Title: Computational Modeling of 60 Hz Subthalamic Nucleus Deep Brain Stimulation for Gait Disorder in Parkinson's disease

Study Description: The goal of this research is to further our understanding and application of deep brain stimulation in Parkinson's patients with gait disorder.

We will assess the degree to which stimulation parameters affect gait parameters. We will test the hypothesis that the addition of levodopa in combination with stimulation produces a synergistic improvement in certain gait domains. In addition, we test the hypothesis that a subject's gait on stimulation can be predicted with statistically significant accuracy using gait measurements on high frequency stimulation. Finally, we will test the hypothesis that the best stimulation frequency, which yields improvement among various gait parameters, can be predicted using objective sensor data collected at baseline

Objectives:

Aim 1: To determine the impact of 60Hz subthalamic deep brain stimulation on gait kinematics using wearable sensors

- Aim 1.1: To determine whether 60Hz STN-DBS elicits a differential response in gait kinematics compared to high frequency
- Aim 1.2: To determine the influence of 60Hz STN-DBS and levodopa on gait kinematics

Aim 2: To develop machine learning models to predict optimal subthalamic deep brain stimulation frequency based on wearable sensor profiles of baseline Parkinson's motor symptoms

- Aim 2.1: To develop machine learning models to predict gait response to 60Hz stimulation without additional testing
- Aim 2.2: To develop machine learning models to predict best stimulation frequency (60Hz vs. high frequency).

Endpoints:

Primary Endpoints:

Gait parameters:

- Postural sway – root mean square (RMS) sway in antero-posterior (AP) and medio-lateral (ML) planes;
- Gait – cycle duration (seconds), speed (m/s), stance (%), swing (%), heel strike angle (degrees), toe off angle (degrees), stride length (cm), cadence (steps/min), step duration (seconds), elevation at midswing (cm) (foot clearance), double support (%), arm swing velocity (deg/s), and range of motion (degrees);

- Circumduction – turn angle (degrees), turn duration (seconds), and turn velocity (deg/s).

Machine learning models to: 1) predict gait kinematics on 60Hz STN-DBS; 2) predict best stimulation frequency using wearable sensor data collected at baseline.

Secondary Endpoints:

Tremor (rest, kinetic, postural)

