Aim 2.2. Similar to Aim 2.1, in this sub-Aim we conduct regression analysis to predict gait parameters. However, in this sub-Aim, gait parameters are predicted on low and high frequency in the context of ON and OFF medication conditions using baseline bradykinesia, tremor, and gait sensor measurements, plus MDS-UPDRS III rigidity and axial sub scores. Patient and disease characteristics will be used as regressors. Again, models will be based on RF classifier, where other modeling techniques, such as neural networks, will be used as benchmarks. The best performing parameters identified in Aim 2.1 will be used to guide the model building in this sub-Aim. Also, aforementioned performance enhancing techniques will be used, if possible, and confidence intervals will be generated using bootstrapping. These models will be able to predict the best stimulation frequency and contact pairs for the patient immediately after baseline evaluations and provide a confidence level. Similar to Aim 2.1, we will

develop these models with and without accounting for PD medications to further quantify their impact and provide additional options for patients.

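### The text gives no rule for turning Aim 2.2's predicted gait parameters into one best frequency, so the plan does not test that primary claim

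*Combined protocol and SAP*

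**What the plan says.** The synopsis (Section 1.1) lists, among the primary endpoints, a machine learning model that predicts the best frequency from baseline sensor data. Section 9.1 describes that target as "the best stimulation frequency (60Hz or HFS stimulation), which yields improvement among various gait parameters" and goes no further.

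For Aim 2.2, Section 9.4.2 says "in this sub-Aim we conduct regression analysis to predict gait parameters", at low and high frequency and with and without medication. It then concludes: "These models will be able to predict the best stimulation frequency and contact pairs for the patient immediately after baseline evaluations". Section 2.3.3 mentions a ranking but does not say how it is formed.

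Each patient is tested at four contact pairs and two frequencies in each medication state (Section 4.1: "total of 8 trials with each contact pair being either LFS or HFS, exclusively"). For validation, Section 9.4.2 names cross-validation, with leave-one-out as an example, and bootstrapping. It does not say whether the unit left out is a patient or a single measurement row. The Holm-Bonferroni adjustment ("adjust for multiple comparisons for the 20 outcome measures") is stated for Aim 1.1 only.

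The earlier study by the same team used the frequency chosen clinically and kept for about 12 months as its label (Sections 4.2 and 9.1). Aim 2.2 does not adopt that label.

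**The concern.** Three things are missing between the regressions and the claim they are meant to support.

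- **A label.** The text gives no direction of improvement per parameter, no primary parameter or composite, no weights, no minimum difference, no tie rule, and no way to combine contact pairs. Two analysts following the plan could label the same patient oppositely.
- **A test of the right quantity.** Best frequency depends on the sign of a within-patient difference. The plan assesses gait level at each frequency, and level can be predictable when the difference is not.
- **Protection against late choice.** Section 10.1.4 sends data to the modelling team as each subject finishes, and the amendment history (version 1.8) records interim modelling on 10 subjects. Modelling therefore began with no label rule in the readable text.

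At stake is whether a reported accuracy for best frequency means anything for the randomized trial that this study is intended to prepare (Section 2.1).

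**Working it through.** **The plan's own figure.** Section 9.2 gives 15.79 × 0.03 / 0.14² = 24.17, taken as 24. Adding 20% gives 24 × 1.2 = 28.8, so 29, and the final number is 30. This reproduces. It rests on gait speed in healthy people against patients, so it sets no accuracy target for Aim 2.2. I use n = 24 and n = 30 below only as the available sample sizes.

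**Number of candidate labels.** Section 1.1 lists 2 sway, 13 gait and 3 turning measures: 2 + 13 + 3 = 18. The Aim 1.1 list in Section 9.4.2 also counts to 18, although the text there says 20. I use 18.

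**Does the rule matter?** Take a patient's 18 differences between frequencies, each oriented so that positive means better at 60 Hz. Assume they are normal with no mean effect and a common correlation r. The documents give no such data, so r is varied.

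- The correlation of one parameter with the equal-weight mean of all 18 is √[(1 + 17r)/18]. The two labels disagree with probability arccos(that value)/π. At r = 0.5: √(9.5/18) = 0.726, so 24% of patients. The figures are 30% at r = 0.3, 18% at 0.7 and 10% at 0.9.
- One parameter at four contact pairs gives four signs. At r = 0.5 across pairs, all four agree with probability 2/5 = 40%, so they conflict in 60% of patients (46% at 0.7, 26% at 0.9).

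**Level against difference.** Let baseline B have variance 1, and let gait at each frequency be 0.9B plus an independent error of variance 0.19 (the 0.9 is an assumption). Baseline then explains 0.9² = 81% of the variance at each frequency. The difference between frequencies contains only the two errors, so baseline explains 0% of it. Both regressions look strong, yet the predicted better frequency is no better than a coin toss.

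**Chance of apparent success from an uninformative model.** The test is one-sided at 5% against 50% correct.

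- One fixed label, n = 24: at least 17 correct are needed, and P(X ≥ 17 | 24, 0.5) = 3.2%.
- One fixed label, n = 30: at least 20 correct are needed, and P(X ≥ 20 | 30, 0.5) = 4.9%.
- Best of 18 independent labels: 1 − (1 − 0.03196)^18 = 44% and 1 − (1 − 0.04937)^18 = 60%.
- Best of 18 correlated labels (4,000 simulated trials per setting, coin-toss predictions):

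| Assumed r | n = 24 | n = 30 |
|---|---|---|
| 0.3 | 35% | 49% |
| 0.5 | 30% | 41% |
| 0.7 | 25% | 31% |
| 0.9 | 15% | 21% |

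**Unit of cross-validation.** Each patient contributes 8 settings × 2 medication states = 16 rows. In Aim 2.2 the baseline predictors describe the patient, not the stimulation setting. If single rows are left out, the same patient's other rows stay in the training data, and performance in a new patient is not measured.

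**The case against.** Several counter-arguments have force.

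- Prediction error for each gait parameter needs no label. Section 9.1 also attaches its claim of statistical significance to Aim 2.1, and says of Aim 2.2 only that best frequency can be predicted. This stands. A reader might infer that nothing in Aim 2.2 can be computed or assessed, but only the last step is undefined.
- Figure 2 is captioned as the overview of the Aim 2 analysis and could not be read. It might contain a rule. The text describing Aim 2 does not state one.
- A reader might infer that most patients have no label because their 18 parameters rarely all agree (about 10% do at r = 0.5). The plan does not require unanimity, and a simple majority vote would tie in only about 5% at that correlation.
- A reader might also apply the chance of a nominal p < 0.05 among 18 mean comparisons. Those tests belong to Aim 1.1, which has its own adjustment.
- No passage says the label will be picked to suit the results. Aim 2 is developmental, with cross-validation and bootstrapping planned. That is fair, but neither technique corrects for choosing the target afterwards.
- Gait speed is not singled out by the documents as the right label. Section 9.2 sized the study on healthy against patient speed, not on one frequency against the other.

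**Conclusion.** The concern holds in a limited form. The readable text does not say how predicted gait parameters become one best frequency, and it does not assess the within-patient difference on which that label depends. The statement in Section 9.4.2 that the models predict best frequency is therefore not tested by the plan.

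If the label were chosen afterwards from 18 single-parameter candidates, false apparent success would rise from 3.2% to between 15% and 44% at n = 24, and from 4.9% to between 21% and 60% at n = 30, for correlations from 0.9 down to independence. These ranges assume no mean effect, equal correlation between parameters and a comparison with 50%. Some parameters are tied nearly by definition (stance and swing, cycle duration and cadence), so equal correlation is a simplification.

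The figures show what the gap permits. They are not evidence that a label has been or will be chosen in this way, because the documents do not say when a rule was or will be set.

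**What to change.** Before the final models are run, add to Section 9.4.2:

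1. One analysis label per medication state. This can be the sign of the HFS-minus-60 Hz difference in one named parameter (gait speed is one defensible choice), or in a composite with stated directions and weights.
2. How the four contact pairs are combined, for example by the mean difference over pairs.
3. A minimum difference or a tie rule.
4. Evaluation of the predicted within-patient difference and its sign, with all rows of a patient held out together.
5. Accuracy reported against always choosing the more common label, since 50% is too low a bar when labels are unbalanced.
6. Other parameters and label rules reported as supportive.

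The report should also state that modelling on 10 subjects preceded the rule. If Figure 2 already holds a rule, it should be written into the text.

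This defines a label for analysis only and says nothing about how any patient should be programmed. It costs wording, with no new data or visits. The downsides are that a single label gives less weight to other gait domains, and that the reported accuracy may be lower.
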